#### **7. Costs**

There will be no costs to the participant for participating in this research study.

#### **8. Consent process and documentation**

FQHC partners will query their EHR systems and provide a list of eligible patients and their contact information to their outreach staff, who will call patients, verify eligibility, and read a consent script over the phone. All participants will provide verbal consent over the phone. We are requesting a waiver of documentation of consent and a waiver of HIPAA authorization due to practical concerns of obtaining written consent over the phone and the minimal-risk nature of the study.

**NCT Number**

**NCT06124131**

**Statistical Analysis Plan Date:**

**3/11/2024**

**BENEFIT-C Statistical Analysis Plan.** Analyses for the primary outcome will test the between-group difference in the proportion of participants who completed a colorectal cancer screening at 2-month follow-up. Secondary outcomes will test between-group differences in the proportion of participants completing a flu shot, COVID-19 shot, any of the three services, and all three services at 2-month follow-up. Analyses will use a chi-squared test of independence or a Fisher's exact test, as appropriate based on achieved cell sizes. We will also test for statistically significant between-group differences in baseline characteristics, and if necessary, adjust for them in a follow-up sensitivity analysis using multivariable logistic regression.

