Using a 2-arm randomized controlled trial design, we will test the effectiveness of patient financial incentives for enhancing routine outreach for preventive health services, namely colorectal cancer screening, flu vaccines, and COVID-19 vaccines. FQHC patients who are aged 45-75 years old and due for a colorectal cancer screening (up to n=100) will be identified through the electronic health records of our FQHC partners. Participants who meet eligibility criteria and enroll in the study will be randomized to one of two arms: the control arm will receive outreach by FQHC staff to encourage completion of a stool-based colorectal cancer screening provided by the FQHC as well as flu and COVID-19 vaccination. They will receive \$50 financial incentives/service for completion of flu and COVID-19 vaccines. The intervention arm will receive the same patient outreach and flu/COVID-19 incentives and will also be offered \$50 financial incentives for completion of colorectal cancer screening.

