### **2. Subject Population**

Using the following criteria, we will enroll up to 100 patients at partner FQHCs:

Inclusion criteria: Age 45 to 75; receive care at a participating FQHC; due for a colorectal cancer screening; ability to understand and speak English

Exclusion criteria: currently participating in another clinical trial or research study on colorectal cancer screening; unable or unwilling to give informed consent

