### **3. Procedure**

After obtaining verbal consent, FQHC outreach staff will verify eligibility and consent participants. The FQHC staff will then read either the intervention or control script depending on the random group assignment of each participant. The script for the control group will follow standard clinical practice for scheduling colorectal cancer screening (a stool-based test), flu and COVID-19 vaccination. The script will offer financial incentives (\$50 per service) for completing flu and COVID shots. The script for the intervention group will be adapted from the control script to include the offer of financial incentives (and additional \$50) for completion of colorectal cancer screening. Study staff will verify completion of each preventive service via weekly limited EHR data downloads for participating patients. After a 2-month follow-up period, a final EHR download will be obtained. The primary outcome is the difference in proportion of participants completing colorectal cancer screening between the two groups. All electronic data will be stored on secure cloud-based servers and accessed on HIPAA-compliant, encrypted, password-protected computers that are only accessible to the FQHC and study staff.

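### When completion is low enough to trigger the SAP's Fisher fallback, that test is very conservative; putting Boschloo's test in that branch only cannot lose power and, with near-equal arms, can gain some (minor)

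*SAP*

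**What the plan says.** The SAP, a single paragraph, sets one testing rule for every outcome: "Analyses will use a chi-squared test of independence or a Fisher's exact test, as appropriate based on achieved cell sizes". It covers the primary analysis, which is to "test the between-group difference in the proportion of participants who completed a colorectal cancer screening at 2-month follow-up", and the secondary outcomes, the "proportion of participants completing a flu shot, COVID-19 shot, any of the three services, and all three services at 2-month follow-up".

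On size, Protocol section 2 gives a ceiling: "we will enroll up to 100 patients at partner FQHCs". Protocol section 1 describes two arms. Neither document states the allocation ratio, the significance level, sidedness, expected completion rates, a power target, or what cell size moves the analysis from chi-squared to Fisher.

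**The concern.** Fisher's test treats the total number of completers as fixed. This design fixes only the arm sizes, and the total is random. With about 50 per arm and few completers, the conditional distribution has so few attainable values that the real type I error falls far below 5%, and power falls with it.

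Boschloo's test uses the Fisher p-value as its statistic but calibrates it over the unknown common completion rate. Applied to all tables, it keeps type I error at or below 5% at every rate. It rejects every table that Fisher rejects, plus some others.

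At stake is a real difference being reported as non-significant because of the fallback test named. The likeliest place is the all-three-services outcome, since its rate cannot exceed that of the least-used service. With at most 100 participants and no sample size derivation, there is little power to spare.

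**Working it through.** The plan has no power or size figure to reproduce, so the check is a full enumeration.

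**Inputs**
- Total of 100 in two arms: Protocol sections 1 and 2.
- 50 per arm: assumed; other splits are checked in step 5.
- Two-sided 5%: assumed.
- Completion rates: assumed, because the documents give none.
- Trigger for Fisher: not defined, so two readings are used (any expected count below 5; any observed count below 5).

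**Method.** For each of the 51 × 51 tables (x, y), the probability is Bin(x; 50, p1) × Bin(y; 50, p2). Size is the sum over rejected tables with p1 = p2. Power is the same sum with p1 ≠ p2. Boschloo's region is all tables with Fisher p ≤ c, where c is the largest cut-off whose maximum size over the common rate is ≤ 5%. At 50/50, c = 0.0693 and the maximum size is 4.87%. Since c exceeds 0.05, Boschloo's region contains Fisher's.

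**1. When the Fisher branch is reached.** With m completers in total at 50/50, the smallest expected count is min(m, 100 − m) × 50/100. This is below 5 when m < 10 or 100 − m < 10.

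**2. True size at 50/50**

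| Common rate | Fisher | Boschloo |
|---|---|---|
| 4% | 0.42% | 1.48% |
| 6% | 1.01% | 2.59% |
| 10% | 1.79% | 3.22% |

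**3. Single tables.** For 0/50 v 5/50, Fisher's two-sided p = 2 × C(50,5)/C(100,5) = 2 × 2,118,760/75,287,520 = 0.056; Boschloo gives 0.035. For 1/50 v 7/50 the values are 0.059 and 0.037. Both tables have expected counts below 5 (2.5 and 4), so both readings send them to Fisher.

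**4. Power of the whole rule at 50/50, changing only the Fisher branch**

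| Rates | Chance of an expected count < 5 | Expected-count trigger: SAP → amended | Observed-count trigger: SAP → amended |
|---|---|---|---|
| 2% v 12% | 84% | 34.8 → 46.3 (+11.5) | 31.3 → 44.1 (+12.8) |
| 4% v 16% | 45% | 48.1 → 53.2 (+5.1) | 37.1 → 46.4 (+9.3) |
| 5% v 20% | 18% | 64.3 → 66.3 (+2.0) | 51.5 → 58.4 (+6.9) |

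At 20% v 40% the expected-count trigger is practically never met and the observed-count trigger is met in about 2% of trials, so the gain is about nil.

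**5. Other splits (control/intervention), Fisher for all tables v Boschloo for all tables, 2% v 12%**
- 48/52: 35.2% v 48.3%
- 45/45: 26.1% v 38.2%
- 40/40: 19.7% v 31.7%
- 45/55: 40.2% v 41.2%
- 53/47: 51.3% v 51.7%

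At 48/52 Fisher's size is 1.9%, 2.5% and 3.1% at common rates of 4%, 6% and 10%, so it is less conservative than with exactly equal arms.

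**6. Size of the whole rule at 50/50.** The maximum is 5.69% under the SAP's rule and 5.69% after the change. It arises in the chi-squared branch, which the change leaves alone.

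**The case against.** The strongest reply is that the SAP's plan is conventional and valid: Fisher controls type I error, and choosing a less common exact test is an optimisation. That stands, and it is why the point is minor.

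Three stronger readings are tempting, and the documents support none of them.

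- A reader might infer a general loss of about 8 to 13 points at this sample size. Figures of that order compare Fisher for every table with Boschloo for every table, at low rates and near-equal arms. The SAP applies Fisher only to small cells. Under the expected-count reading, two of the three scenarios in step 4 reach Fisher in fewer than half of trials, and the gain shrinks to 5.1 and 2.0 points.
- A reader might infer that the amended rule guarantees 5%. That guarantee belongs to Boschloo applied to all tables, not to a mixture with chi-squared.
- A reader might infer that the primary outcome is affected. No completion rate appears anywhere. Under the expected-count reading at 50/50, screening would need fewer than 10 completers, or fewer than 10 non-completers, among 100.

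An opposite objection is that Boschloo can lose power against the SAP's rule. It can if used for every table: at 5% v 20% it gives 58.3% against 64.3% under the expected-count trigger, 6.0 points less. That is a different change from the one recommended here. Replacing only the Fisher branch adds rejected tables and removes none.

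**Conclusion.** The point holds in a conditional form and is minor. When completion is low enough for the Fisher branch to be used, the named fallback is very conservative, and a test that rejects everything Fisher rejects and more is available.

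At 50/50 and two-sided 5%, in the three low-rate scenarios examined, the gain over the SAP's own rule is about 2 to 12 points with an expected-count trigger and about 7 to 13 with an observed-count trigger. It vanishes at moderate rates and can be 1 point or less in some unequal splits. The rates, the split, the level, the sidedness and the trigger are all assumptions. That the change cannot reduce power rests on none of the assumed rates: it follows from one rejection region containing the other.

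**What to change.** In the SAP's sentence on tests, replace the reference to Fisher's exact test with: Boschloo's unconditional exact test (two-sided, 5%). It would apply to every outcome for which chi-squared is not used. Make the change before outcome data are seen; moving to a more powerful test afterwards would not be credible.

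The cost is one phrase, and standard software provides the test. The downside is that some readers will not know it, which a footnote giving Fisher's p-value would meet.

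The amended text should not claim strict 5% control for the combined rule. If strict control is wanted, Boschloo would have to be used for all tables, at the price in power shown above where chi-squared would otherwise apply.
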